**Abstract**

MS (Multiple Sclerosis) is the most common neurological disease involving disabilities in young adults, with bowel symptoms such as constipation and fecal incontinence. The main objectives of the study are to assess the prevalence, characteristics, severity and impact on the Quality of Life of intestinal disorders in this population, to correlate the severity and characteristics of constipation and fecal incontinence with Intestinal Transit Time and the time dedicated to the evacuation, and how these items change in relation to the use of transanal irrigation (TAI). Another objective is to identify the composition of the intestinal microbiota in MS patients in relation to the type of bowel characteristics, comparing it with microbiota profile of the healthy population of the same region of origin, Emilia-Romagna, Italy.

**Study Protocol**

MS (Multiple Sclerosis) is the most common neurological disease involving disabilities in young adults, with Central Nervous System involvement in both the brain and spinal cord. In a recent review, its incidence in the United Kingdom is estimated at 7 new cases per 100,00 inhabitants per year, with a prevalence of about 100,000 patients. Bowel symptoms, in particular constipation and faecal incontinence, affect more than two thirds of MS patients, and have a significant impact on patients' quality of life (QoL) by significantly limiting their social, occupational and emotional life.

Recently, bowel management based on Transanal Irrigation (TAI) has also been proposed in patients with MS, but TAI efficacy on intestinal transit time and patient's compliance with TAI have not been defined yet.

The primary objective of the study is to assess the prevalence, characteristics, severity and impact on the Quality of Life of intestinal disorders in patients who consecutively refer to the neurological clinic for the diagnosis and treatment of Multiple Sclerosis at Ferrara University Hospital, Italy.

Secondary objectives are to correlate the severity and characteristics of constipation and fecal incontinence with intestinal transit time and the type of faeces evacuated according to the Bristol Stool Form Scale; to evaluate the costs in terms of the precautions (diapers, traverses, drugs, medicated clysm, etc.) and the time dedicated to the evacuation, and how these items change in relation to the use of TAI; and finally, to study the composition of the intestinal microbiota in MS patients in relation to the type of bowel characteristics, comparing it with the profile of the healthy population of the same region of origin, Emilia-Romagna, Italy.

The study proposed is a monocentric prospective observational study. The study population will be composed of patients who will consecutively refer to the Neurological Clinics of the University Hospital of Ferrara, Italy for a number of about 150 patients.

The study will consist of two phases. The first phase will be the selection of eligible patients by administering two self-filling questionnaires: PacQol (Patient Assessment of Constipation Quality of Life) and NBD (Neurogenic Bowel Dysfunction Score).

Patients with PacQol score  $\geq 32$  will be sent to the surgical clinic for the second phase. During the latter phase, patients will undergo a number of visits varying from 1 to 4 depending on the patient's willingness to continue the study. After the illustration of the purpose and protocol of the study to the patient,

classification of constipation and/or faecal incontinence in accordance with the Rome III Diagnostic Criteria will be assessed, with consideration of other possible etiopathogenetic factors other than MS. Further questionnaires will be filled in to evaluate the disease status (Constipation scoring system by Agachan-Wexner, Obstructed defecation score by Altomare et al, Fecal Incontinent grading scale by Jorge-Wexner); if the patient will consent to the continuation of the study, he will be given 7-days food diaries, evacuation diaries, radiopaque markers, stool collection container and appointment date for plain abdominal X-ray which may coincide with the appointment for examination number 2 (visit 2 or 3).

In particular, radiopaque markers Intestinal Transit Study will be performed according to the Bouchoucha procedure revised by Abrahamsson, which involves ingestion of 10 markers for 6 days at the same time and execution of a plain abdominal X-ray on the 7th day. During this week the patient will complete an evacuation diary recording the time and number of evacuations, the method of eventual bowel care, the consistency of faeces according to the Bristol Scale, any episode of fecal incontinence, the type of hygiene measures in general, the number of enemas, diapers, and any other garrison used in relation to the evacuation.

Patients will be asked to collect a faecal sample in a container during the last week before the following inspection at Visit 2.

During the second visit, the outcome of the plain abdominal X-ray will be discussed, the completed diaries will be collected, and the faecal sample will be stored at -20 C° and subsequently sent to the Laboratory of the Department of Pharmacy and Biotechnology of the University of Bologna, Italy for the analysis of the intestinal microbiome composition.

Patients with severe NBD impairment will be offered the adoption of TAI as a way to manage their own evacuation, replacing any other measure used until that moment (suppositoires, enemas) with the exception of the possible intake of macrogols and/or prebiotics and/or probiotics which instead can be continued. This treatment will be proposed to all patients with severe impairment of intestinal function.

The TAI training with Peristeen will be carried out at the surgical clinic of the Surgical Department of the Ferrara University Hospital, Italy, by the personnel involved in the study, usually in a single session, but more sessions may be necessary.

During the following 4 weeks, patients will continue to use the Peristeen at home according to the instructions provided by the training staff collecting a stool sample each week. During the last of the four weeks of TAI use patients will repeat the compilation of food diaries, evacuation diaries, the radiopaque markers Transit Time, and collection of the stool for microbiota analysis. The appointment for the radiography could coincide also in this case with the following visit (visit 3 or 4).

During the last visit the outcome of Transit Time X-ray will be discussed, completed diaries and stool samples will be collected, and PAC-QoL questionnaire will be submitted to patients who completed the study pathway.

Patients will be asked about overall satisfaction of TAI treatment with Peristeen by means of a numerical assessment from 0 to 10.

Finally, any comment will be noted as well any events that might be related to TAI irrigation with Peristeen will be recorded.

Patients will undergo a neurological examination 3 months after the start of treatment.

The whole duration of the study will be of 2 years.

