## **Intervention**

Patients with severe intestinal dysfunction impairment (PAC QoL score  $\geq 32$ ) will be offered the adoption of the TAI (Transanal Irrigation) with Peristeen Device as a way to manage their own evacuation, replacing any other measure used until that moment (suppositoires, enemas) with the exception of the possible intake of macrogols and/or prebiotics and/or probiotics which instead patients can continue. This treatment will be proposed to all patients with severe impairment of intestinal function.

The TAI training with Peristeen will be carried out at the surgical clinic of the Surgical Department of the Ferrara University Hospital, Italy, by the health personnel involved in the study, usually in a single session, but more sessions may be necessary, documented in CRF as VISIT 3, VISIT 3 bis and so on, until the end either with the continuation of the TAI independently for 4 weeks or with patient's exclusion from the study if the guarantees of appropriate use of the device will not be reached.

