## **Secondary Outcome Measures**

- 1) Correlation between Intestinal Transit Time and constipation scores in MS patients with intestinal dysfunction. To calculate the Correlation Coefficient between Intestinal Transit Time and the Bristol Score, the Agachan-Wexner Score, the Cleveland Clinic Index, and the NBD Score.
- 2) Correlation between Diet and intestinal dysfunction in MS patients. To correlate the Intestinal Transit Time and the Bristol Scale Score to the type of diet usually followed by patients in terms of adequacy of caloric intake compared to BMI, composition of macronutrients, and dietary fibre intake.
- 3) Efficacy of TAI in MS patients with intestinal dysfunction. Compare the Scores of the assessment scales used before and after the 4-week TAI treatment period, in order to detect a reduction in severity and an improvement in QoL score. Calculate a possible advantage or non-benefit of the costs of treatment with TAI compared to the previous bowel management.
- 4) Analysis of Microbiota in MS patients with intestinal dysfunction, before and after treatment with TAI. Compare the composition of the intestinal microbiota of MS patients with the known "healthy"

profile of the Italian population of North East of Italy and assess any changes after the period of treatment with TAI.

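### The cost comparison for TAI is at risk of bias towards TAI: as written it rests on successful users, and no training, device or consumable cost is assigned to it

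*Combined protocol and SAP*

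**What the plan says.** The cost objective in the Study Protocol section is "to evaluate the costs in terms of the precautions (diapers, traverses, drugs, medicated clysm, etc.) and the time dedicated to the evacuation", together with the change in these items under TAI. Secondary Outcome Measures, item 3, gives the comparison: "Calculate a possible advantage or non-benefit of the costs of treatment with TAI compared to the previous bowel management".

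TAI is adopted by "replacing any other measure used until that moment (suppositoires, enemas) with the exception of the possible intake of macrogols and/or prebiotics and/or probiotics". Before TAI, a seven-day diary records, among other things, "the number of enemas, diapers, and any other garrison used in relation to the evacuation". The on-TAI counterpart is a single week: "During the last of the four weeks of TAI use patients will repeat the compilation of food diaries, evacuation diaries".

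The Intervention section says training takes place "usually in a single session, but more sessions may be necessary, documented in CRF as VISIT 3, VISIT 3 bis and so on". A patient who cannot be brought to reliable use of the device is excluded from the study. The Statistical analysis section gives no method for costs: no unit prices, perspective, time horizon or rule for excluded patients.

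**The concern.** Adopting TAI uses resources before any benefit can appear: one or more supervised sessions, and then a device with consumables. Some of those resources go to patients who never become users. The week-four diary comes after training has ended and exists only for patients who continued, so neither kind of cost falls inside the window or the group in which costs are measured. The items named in the objective are existing precautions and evacuation time, and an analyst working from that list has no instruction to add anything specific to TAI.

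At stake is the statement on cost advantage or non-benefit. A clinic deciding whether to offer TAI needs the cost per patient who starts. A figure from those who succeeded could show a saving that shrinks, or disappears, once everyone who was trained is counted.

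**Working it through.** The documents give no cost figure, so there is nothing to reproduce. The check sets the passages side by side and then uses algebra to see which way the gaps push.

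**Coverage of each cost component**
- Enemas, diapers and other aids: in both diaries (Study Protocol section).
- Evacuation time: named in the cost objective, with no rule for pricing it.
- Training sessions: documented in the CRF (Intervention section), not assigned to the cost outcome.
- Device and consumables: not named in the objective; possibly meant by the wording of item 3.
- Patients who fail training: excluded, with no on-TAI diary planned. At most 50 patients are invited to the second phase (Group Cohort section), so each failure removes at least 1/50 = 2% of those who start.

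**Notation** (none of these values is in the documents)
- E: weekly cost of the replaced enemas and suppositories.
- C: weekly change in all other listed items, including evacuation time if priced.
- T: weekly cost of device and consumables.
- f: share of starters who fail training.
- K: mean training cost per starter, failures included.
- H: weeks over which training is spread.

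Patients who fail are assumed to return to their baseline costs. Differences are TAI minus previous management, so a negative value is a saving.

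**Narrow reading: listed items only, successful users only**
- N = C − E

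**All starters, all components**
- F = (1 − f)(T + C − E) + K/H

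**Gap between them**
- N − F = f(C − E) − (1 − f)T − K/H

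If the listed items show a saving (C < E), none of the three terms is positive, so the narrow reading flatters TAI. If they show an added cost, for example because irrigation lengthens evacuation, the first term turns positive and can offset the other two.

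**Broad reading: device and training counted, but successful users only**
- B = T + C − E + Ks/H, where Ks is the training cost per successful user.
- With Kf the training cost per failure, K = (1 − f)Ks + f·Kf, so F = (1 − f)B + f·Kf/H.
- B − F = f(B − Kf/H)

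Selection therefore remains even if every TAI cost is counted in the completers. It favours TAI whenever B shows a saving, and reverses only if B is a net added cost larger than Kf/H.

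**Illustration of dependence on prices** (assumed values, not an estimate of magnitude). Take E = 1 unit per week, C = 0 and f = 0. Then N = −1 whatever TAI costs, and F = T − 1 + K/H:
- T = 0, K/H = 0: 0 − 1 + 0 = −1
- T = 1, K/H = 0.25: 1 − 1 + 0.25 = +0.25
- T = 2, K/H = 0.5: 2 − 1 + 0.5 = +1.5

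The conclusion changes sign where T + K/H = 1, and the documents give no means of locating the study on that scale.

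**The case against.** A reader might infer something stronger: that the comparison favours TAI by construction, because it credits TAI with enemas and suppositories stopped by rule while counting nothing for training. The documents do not support that, for four reasons.

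- **Silence is not exclusion.** The list of cost items is open-ended, and item 3 names the cost of TAI treatment and allows a finding of non-benefit. Device and training costs are unspecified; they are not shown to be omitted.
- **Avoided enemas and suppositories are a real saving.** When one method replaces another, the replaced items belong in the cost difference. Item 3 assesses efficacy through scale scores, in a separate sentence, and nowhere treats fewer enemas as evidence of benefit.
- **Only some items are replaced by name.** Diapers and traverses are not named as stopped, macrogols, prebiotics and probiotics may continue, and evacuation time can move either way.
- **The window is symmetric.** Baseline is also one seven-day diary, and comparing weekly running costs is a legitimate choice. Whether to add one-off training depends on perspective and horizon.

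All four stand, and they limit the point to a risk of bias. They do not answer the explicit exclusion of patients who fail training, which restricts the on-TAI data to successful users however the cost list is read.

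**Conclusion.** The point holds as a risk of bias towards TAI in the secondary cost comparison. It rests on three facts in the text: training failures leave the study, the on-TAI diary covers only week four, and neither training sessions nor device and consumables are assigned to the cost outcome.

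Neither the size nor the sign of the bias can be determined from the documents. The gaps favour TAI when the compared items show a saving. Prices, session counts, failure rate and any added evacuation time could alter that, and none is given. The algebra assumes that patients who fail return to their baseline costs. The importance is minor, because the primary outcomes and the before/after scale scores are not touched by this point.

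**What to change.** In Secondary Outcome Measures, item 3, with a matching sentence under Statistical analysis:

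- Compute the cost difference over all patients who began TAI training, including those later excluded.
- Count every training session already documented in the CRF (Visit 3, 3 bis and so on).
- Give patients who failed training their baseline-diary costs plus the cost of their sessions.
- Put device and consumables on the TAI side, and state the unit prices, perspective and horizon used.
- Show weekly running costs and one-off training costs separately, so that readers can apply another horizon.
- Keep avoided enemas and suppositories in the difference, labelled as protocol-driven substitution and not read as efficacy.

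Treatment and visits do not change, and session counts are already recorded; session duration may need adding to the CRF if staff time is to be priced. The cost is slightly more analysis work and a probably less favourable TAI cost figure.

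### The only PAC-QoL score before transanal irrigation is the one that selected the patient, so the before/after comparison contains regression to the mean

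*Combined protocol and SAP*

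**What the plan says.** The Study Protocol section describes two phases. Phase 1 is a screen at the neurology clinic: "The first phase will be the selection of eligible patients by administering two self-filling questionnaires", namely PAC-QoL and the Neurogenic Bowel Dysfunction (NBD) score. Patients with PAC-QoL of 32 or more "will be sent to the surgical clinic for the second phase". Group Cohort and Study population add that the first 50 such patients are asked to continue.

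Before TAI, the Study Protocol lists these assessments:

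- **First phase 2 visit:** "Further questionnaires will be filled in to evaluate the disease status". These are the Agachan-Wexner, Altomare and Jorge-Wexner scales. PAC-QoL is not among them.
- **Week before Visit 2:** radiopaque markers, food and evacuation diaries, stool sample.
- **Visit 2:** X-ray result, diaries and stool sample. No questionnaire is listed.
- **Training:** one or more sessions. No questionnaire is listed.

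At the last visit the "PAC-QoL questionnaire will be submitted to patients who completed the study pathway". Secondary outcome 3, which carries the efficacy label for TAI, is to "Compare the Scores of the assessment scales used before and after the 4-week TAI treatment period", looking for lower severity and better QoL. Statistical analysis names chi-square, t and Mann-Whitney tests. It defines no baseline, names no paired test and does not address selection on the baseline.

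The rule for offering TAI is given twice and differs. Study Protocol: "Patients with severe NBD impairment will be offered the adoption of TAI". Intervention: "Patients with severe intestinal dysfunction impairment (PAC QoL score", with the same cut-off of 32.

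**The concern.** A questionnaire score is partly stable burden and partly the circumstances of the day. Patients chosen because one reading was high will, on average, score lower at the next reading without any treatment. If the high reading is also the baseline, that fall enters the estimated effect.

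The screening score also predates the referral appointment, the first surgical clinic visit, the marker and diary week, Visit 2 and training. Any change over that period is counted as change under TAI. With no untreated group, the study cannot separate these parts.

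This is the only outcome labelled as efficacy of TAI, and the protocol says that the effect of TAI on transit time and compliance with it are not yet defined. A significant fall in PAC-QoL is therefore likely to be read as evidence that TAI works.

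**Working it through.** **Plan's own figure.** There is none to reproduce. The numbers 150 and 50 come without a power or precision calculation, and no PAC-QoL mean, SD, reliability or target change is given.

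**Inputs from the documents.** Cut-off 32; at most 50 patients asked to enter phase 2; significance at p < 0.05 (two-sided assumed, so 2.5% in the direction of improvement).

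**Assumptions.**

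- Scores are normal, with no true change.
- Test-retest correlation r is 0.7 to 0.9.
- The share p scoring 32 or more is one third to two thirds. The lower value borrows 50/150, which is a recruitment cap and not a prevalence. The upper value borrows the protocol's statement that more than two thirds of MS patients have bowel symptoms, which is not the share above 32 either.
- The test is a paired t-test.
- There are 20, 30 or 50 before/after pairs.

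**Expected spurious fall, selection on PAC-QoL only.** In SD units, fall = (1 − r) × φ(c)/p, where c is the normal quantile at 1 − p.

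- p = 1/3: φ(c)/p = 0.364/0.333 = 1.091. Fall = 0.3 × 1.091 = 0.33 (r = 0.7) to 0.1 × 1.091 = 0.11 (r = 0.9).
- p = 1/2: φ(c)/p = 0.399/0.5 = 0.798. Fall = 0.24 to 0.08.
- p = 2/3: φ(c)/p = 0.364/0.667 = 0.545. Fall = 0.16 to 0.05.

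**Chance of a falsely significant improvement.** Simulated with zero treatment effect, at least 10,000 runs per cell:

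| Completers | p = 1/3, r = 0.7 | p = 1/2, r = 0.8 | p = 2/3, r = 0.9 |
|---|---|---|---|
| 20 | 47% | 20% | 8% |
| 30 | 66% | 28% | 10% |
| 50 (ceiling) | 87% | 44% | 13% |

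**If TAI is offered only for severe NBD impairment.** A second instrument then selects as well, and it tends to keep patients whose high PAC-QoL is real. Assume that NBD correlates 0.6 with true PAC-QoL, has independent error, and that half of phase 2 qualifies. The fall becomes 0.23 to 0.07 SD (p = 1/3) or 0.09 to 0.03 SD (p = 2/3). With 20 completers the false-improvement rate is then about 26% to 10%, or 8% to 4%.

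**With a second pre-TAI score as baseline.** If that score is not used for selection and measurement errors are independent between occasions, the expected spurious fall is 0. The simulated false-improvement rate returns to between 2.1% and 3.0% in every scenario.

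**The case against.** The strongest reply is that the effect may be small. Fifty is the number of patients asked to enter phase 2, not the number of before/after pairs. Visits depend on willingness, patients who cannot use the device appropriately leave, and PAC-QoL is repeated only in completers. If most patients exceed 32, the questionnaire is reliable and TAI is offered only for severe NBD impairment, the fall is about 0.03 SD. All of this stands. It limits the size but not the direction, and without a second pre-TAI score the study could not show that the effect was small.

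A second reply is that the case report form may schedule another PAC-QoL. It is not among the documents. If it does, one sentence in the protocol naming that score as baseline would settle the point.

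Three stronger readings are tempting but not supported:

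- **That a false positive is the likely result.** The highest rates need 50 pairs and one third of patients above the cut-off. The documents establish neither.
- **That the whole TAI evaluation is compromised.** Transit time, diaries, costs and the three scales from the first phase 2 visit are not the selecting score. They are affected only through their correlation with PAC-QoL. The three primary outcomes do not use the before/after comparison.
- **That correlating a phase 1 NBD score with a later transit time has the same fault.** A time gap mainly weakens a correlation and is not regression to the mean. The timing of NBD is also not clearly fixed at phase 1, since primary Outcome 2 calculates it in the group scoring 32 or more.

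**Conclusion.** The point holds for the PAC-QoL part of secondary outcome 3. As written, the before value is the selecting score, so the comparison includes regression to the mean plus any change between screening and training, and credits both to TAI. Every TAI patient has passed the PAC-QoL cut-off under either version of the offer rule, so the direction does not depend on which version applies. The size does: about 0.05 to 0.33 SD with selection on PAC-QoL alone, and about 0.03 to 0.23 SD if NBD also selects. Both ranges rest on assumed reliability, share above the cut-off, normality and (for the second) the NBD correlation and share qualifying. The number of completers, also unknown, drives the false-improvement rates. This should be fixed, but it concerns one component of a secondary outcome in a single-centre observational study. It says nothing about whether TAI works.

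**What to change.** 1. Repeat PAC-QoL at Visit 2, before TAI training, and name that score as the baseline for the PAC-QoL part of secondary outcome 3.
2. Keep the phase 1 score for primary Outcome 1 and for selection. Do not drop patients from the before/after analysis because of their Visit 2 score.
3. Reconcile the two rules for the TAI offer in Study Protocol and Intervention, and state which measurement the rule uses. If the offer depended on the new baseline score, selection on the baseline would return.
4. State that re-baselining does not remove placebo response, time trends or completers-only follow-up, and report the result as a change during TAI and not as proof of efficacy.

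The cost is one short self-completed questionnaire at a visit already planned, a line in the visit description and a line in the outcome definition. The reported improvement will probably be smaller. The change must be made before patients start TAI, because a missing pre-TAI score cannot be recovered later.

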## **Statistical analysis**

Data will be expressed as median (interquartile range – IQR 25-75) and mean  $\pm$  standard deviation according to distribution assessed by Shapiro-Wilk test. Categorical data will be presented as numbers. Data will be analysed using Chi-square, t-student, and Mann-Whitney tests as appropriate. Cox regression analysis will be employed to assess independent predictors of improvement of intestinal dysfunction after Transanal Irrigation (TAI). Significance will be considered for values of  $p < 0.05$ . Statistical analysis will be performed with IBM SPSS Statistics for Windows, Version 24.0 (IBM Corp. Armonk, NY: IBM Corp.). The report will comply with the strengthening the reporting of cohort studies.

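### Weekly stool samples are collected during TAI, but the microbiota outcome is only before/after and no within-patient method is named, so weeks 1-3 have no planned use and pairing may be lost

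*Combined protocol and SAP*

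**What the plan says.** The Study Protocol section takes one stool sample before TAI: "Patients will be asked to collect a faecal sample in a container during the last week before the following inspection at Visit 2". For the treatment period it says "During the following 4 weeks, patients will continue to use the Peristeen at home", "collecting a stool sample each week". It then lists, for the last of those weeks, repeat diaries, a repeat transit study and "collection of the stool for microbiota analysis". It does not say whether this last-week stool is the fourth weekly sample or an additional one.

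Item 4 of Secondary Outcome Measures is "Analysis of Microbiota in MS patients with intestinal dysfunction, before and after treatment with TAI". It has two parts: "Compare the composition of the intestinal microbiota of MS patients with the known" healthy regional profile, and "assess any changes after the period of treatment with TAI". Neither part mentions weekly time points, and the first does not say which stool sample is used.

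The Statistical analysis section says "Data will be analysed using Chi-square, t-student, and Mann-Whitney tests as appropriate". The only model named is a Cox regression for predictors of improvement, which does not address stool samples. No paired non-parametric test, repeated-measures method or mixed model appears, and the section does not say whether the t-test is paired.

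**The concern.** The sampling schedule produces a short series per patient (baseline plus four weekly samples), while the outcome uses two time points and the analysis section has no tool for a series. Three things are left undecided: what weeks 1-3 are for, which sample counts as the one after treatment, and how several samples from one patient are to be combined or selected.

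The likely consequence is loss of information. Patients collect three samples at home that no planned analysis uses. If the data fail the Shapiro-Wilk check, the only rank test on the list for a two-point comparison is Mann-Whitney, which treats before and after values as coming from different people. Phase 2 invites at most 50 patients and the number who take up TAI is not given, so precision is scarce.

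**Working it through.** **Nothing to reproduce.** The documents give no effect size, SD, power or sample-size calculation for the microbiota outcome.

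**Inputs**
- From the documents: one baseline sample, four weekly samples on TAI, significance at p < 0.05, at most 50 patients invited to phase 2.
- Assumed: n = 50 on TAI (the most favourable case), two-sided testing, 80% power, normal data, a common SD of 1, and an equal within-patient correlation (ICC) of 0.3, 0.5 or 0.7 between any two samples.

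**Step 1: baseline versus week 4, paired and unpaired.** The detectable difference is (1.96 + 0.84) × √(V/n).
- Paired, V = 2(1 − ICC):
  - ICC 0.3: 2.80 × √(1.4/50) = 0.47 SD
  - ICC 0.5: 2.80 × √(1.0/50) = 0.40 SD
  - ICC 0.7: 2.80 × √(0.6/50) = 0.31 SD
- Unpaired, V = 2: 2.80 × √(2/50) = 0.56 SD. This is the figure the unpaired standard error implies, and it ignores the correlation.
- Unpaired test applied to correlated data: the true standard error is smaller than the one the test uses, so the difference is (1.96 + 0.84 × √(1 − ICC)) × √(2/50) = 0.53, 0.51 and 0.48 SD. The loss against the paired test is therefore somewhat less than 0.56 suggests, but it remains.
- Power of the unpaired t-test at the difference the paired test detects with 80% power: Φ[(2.80 × √(1 − ICC) − 1.96)/√(1 − ICC)] = 0.68, 0.51 and 0.22. Simulation (4,000 runs) gave 0.66, 0.50 and 0.22, and 0.64, 0.47 and 0.22 for Mann-Whitney.

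**Step 2: what weeks 1-3 could add.** With equal correlation, the variance of the change is 2(1 − ICC) for week 4 alone and (1 + 1/4)(1 − ICC) = 1.25(1 − ICC) for the four-week mean. The ratio is 1.25/2 = 0.625, a cut of 37.5% at any ICC. This depends on two conditions.
- *Equal correlation.* If on-treatment samples correlate 0.8 with each other but 0.4 with baseline, the variances are 2 − 2(0.4) = 1.20 for week 4 and 1 + (1 + 3 × 0.8)/4 − 2(0.4) = 1.05 for the mean, a cut of 12.5%. If correlation instead decays geometrically with the gap in weeks (0.3 to 0.8 between adjacent weeks), the cut is 41% to 50%.
- *Constant effect from week 1.* If the effect builds as 0.25, 0.5, 0.75, 1, the mean carries 0.625 of the week-4 effect. Under equal correlation its relative efficiency is (0.625²/1.25)/(1²/2) = 0.3125/0.5 = 0.625. The mean would then need 1/0.625 = 1.6 times as many patients as week 4 alone.

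**Step 3: if samples were pooled as independent.** The plan does not state this; the step shows only what the silence leaves open.
- Four on-TAI samples per patient against a fixed healthy profile: the design effect is 1 + 3 × ICC = 1.9, 2.5 and 3.1. The true error is 2(1 − Φ(1.96/√design effect)) = 0.155, 0.215 and 0.266 instead of 0.05 (simulated 0.166, 0.215 and 0.271).
- Pooled unpaired before/after: the true variance is (1 − ICC) times the assumed one, so the true error is 2(1 − Φ(1.96/√(1 − ICC))) = 0.019, 0.0056 and 0.0003. The test is too conservative.

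**The case against.** The best defence is that the plan already implies a valid analysis. Stool for the microbiota is tied to the last TAI week, there is one baseline sample, and the outcome asks about change after treatment. That gives one pair per patient, and Student's t can be read as including the paired test. A per-patient four-week mean or slope with a paired t-test would also be valid and would use every sample. This stands in part: week 4 is the natural post-treatment sample. But pairing is not stated, no paired rank test is listed for non-normal data, and choosing a summary later would be a post hoc decision.

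Two stronger readings are tempting and should not be drawn.
- A reader might infer that samples must be either wasted or counted as independent patients. A per-patient summary is a third option, and nothing in the documents says that samples will be pooled.
- A reader might infer that the mean of weeks 1-4 should be the main contrast because it is more precise. Step 2 shows that the gain depends on unverified conditions and reverses if the effect builds linearly. The mean also answers a different question from the one in the outcome, which concerns change after the treatment period.

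It is also fair to say that no text commits the laboratory to analysing weeks 1-3. Only collection is planned, so using those samples may carry a laboratory cost.

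**Conclusion.** The point holds as a gap in specification for a secondary outcome. The plan collects more on-treatment samples than its outcome uses, gives weeks 1-3 no purpose, does not identify the post-treatment sample, and names no method that secures within-patient comparison when data are non-normal. No primary outcome is affected.

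The firmest cost is the loss of pairing. At n = 50 and ICC 0.3, 0.5 and 0.7, the detectable difference rises from 0.47, 0.40 and 0.31 SD to 0.56 SD on the unpaired standard error, or to 0.53, 0.51 and 0.48 SD when the correlation is taken into account. The n and ICC are assumptions; fewer TAI users would enlarge all of these figures. If a paired t-test was intended and is used, this loss disappears and only the unused weeks and the undefined samples remain. The 37.5% variance cut from averaging four weeks is conditional and should not be quoted as a general gain. Inflated error against the healthy profile would arise only under pooling, which the plan does not state.

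**What to change.** Add one paragraph to the Statistical analysis section, before any microbiota data are analysed:

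1. Say whether the last-week stool is the fourth weekly sample, name it as the post-treatment sample, and state what weeks 1-3 are for.
2. For microbiota measures (transformed abundances and diversity indices), replace the listed tests by a linear mixed model with week (0, 1, 2, 3, 4) as a categorical fixed effect and patient as a random effect.
3. Keep week 4 versus baseline as the main contrast. Give the mean of weeks 1-4 versus baseline and the linear trend over weeks as secondary contrasts.
4. Use only the baseline sample in the comparison with the healthy profile, so that each patient counts once and treatment does not enter.
5. State how missed weekly samples are handled. The mixed model can keep patients who miss a week.

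The cost is slightly more analysis work, with no new visits, patients or collections. If weeks 1-3 were not going to the laboratory, using them adds up to three analyses per TAI patient (at most 3 × 50 = 150). If that is not wanted, specify a paired baseline versus week-4 analysis, with a paired t-test or Wilcoxon signed-rank test, and say that weeks 1-3 will not be analysed.
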